PK sample			X						X	At visits where study drug will be administered, PK samples should be collected prior to administration of study drug.	

Abbreviations: AE = adverse event; AESI = adverse events of special interest; BP = blood pressure; d = days; ETV = Early Termination Visit; EQ-5D-Y = European Quality of Life-5 Dimensions-Youth; ESR = erythrocyte sedimentation rate; ETV = Early Termination Visit; HbAb = hepatitis B core antibody; HBV = hepatitis B virus; hsCRP = high-sensitivity C-reactive protein; IBD = inflammatory bowel disease; JIA = juvenile idiopathic arthritis; LEI = Leeds Enthesitis Index; NK = natural killer; PPD = purified protein derivative; PK = pharmacokinetics; TV = treatment visit; V = study visit; W = study week, WOCBP = women of childbearing potential.

Table RHCG.2.3. Schedule of Activities – Long Term Extension Period (V30 through V42)

Notes: Due to blood volume restrictions, some laboratory tests may not be collected. Laboratory samples are recommended to be collected as described in the sponsor-provided weight-based prioritization chart.														
Visit No	V30	V31	V32	V33	V34	V35	V36	V37	V38	V39	V40	V41	V42	Notes
Study Week	W108	W112	W116	W120	W124	W128	W132	W136	W140	W144	W148	W152	W156	
Study Days (Approximately)	756 ± 7d	784 ± 7d	812 ± 7d	840 ± 7d	868 ± 7d	896 ± 7d	924 ± 7d	952 ± 7d	980 ± 7d	1008 ± 7d	1036 ± 7d	1064 ± 7d	1092 ± 7d	
Treatment Visits			X		X	X		X	X		X	X		Treatment visits are intended only for the dispensation and on-site administration of ixekizumab for the participants CCI [REDACTED] [REDACTED] who have opted for on-site administration.
Immunization record	X			X			X			X				Immunizations occurred during the participation in the study.
Physical examination	X			X			X			X			X	Excluding pelvic, rectal, and breast examinations.
Height	X			X			X			X			X	
Weight	X	X	X	X	X	X	X	X	X	X	X	X	X	Weight will be recorded for every participant at every visit in the Study Drug Administration Log: • For participants CCI [REDACTED] weight will be recorded by study personnel. • For participants CCI [REDACTED] ○ At-home administration: weight will be recorded by the participant or caregiver in the Study Drug Administration

Notes: Due to blood volume restrictions, some laboratory tests may not be collected. Laboratory samples are recommended to be collected as described in the sponsor-provided weight-based prioritization chart.														
Visit No	V30	V31	V32	V33	V34	V35	V36	V37	V38	V39	V40	V41	V42	Notes

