Notes: Due to blood volume restrictions, some laboratory tests may not be collected. Laboratory samples are recommended to be collected as described in the sponsor-provided weight-based prioritization chart.														
Visit No	V30	V31	V32	V33	V34	V35	V36	V37	V38	V39	V40	V41	V42	Notes
Study Week	W108	W112	W116	W120	W124	W128	W132	W136	W140	W144	W148	W152	W156	
Study Days (Approximately)	756 ± 7d	784 ± 7d	812 ± 7d	840 ± 7d	868 ± 7d	896 ± 7d	924 ± 7d	952 ± 7d	980 ± 7d	1008 ± 7d	1036 ± 7d	1064 ± 7d	1092 ± 7d	
Treatment Visits			X		X	X		X	X		X	X		Treatment visits are intended only for the dispensation and on-site administration of ixekizumab for the participants CCI [REDACTED] who have opted for on-site administration.
Rating Scale														
Morning Joint Stiffness Duration	X			X			X			X			X	
Laboratory Tests														
Acute phase reactant (hsCRP)	X			X			X			X			X	
Acute phase reactant (ESR)	X			X			X			X			X	To be performed locally.
Administer TB test(s) (if applicable)	TB testing required only based on clinical assessment of TB risk and according to local regulations and/or local standard of care (Section 9.4.6; Appendix 2). QuantiFERON®-TB Gold, T-Spot or PPD (if applicable) (Section 9.4.6; Appendix 2). PPD to be read locally.													
HCV antibody	X													HCV antibody positive results require a follow-up test for HCV RNA. See Section 9.4.4 for details.
HBV (HBsAg, HBcAb, HBsAb)	X													See Section 9.4.4 for details.
HBV DNA (if applicable)	X			X			X			X			X	Positive for HbcAb require a follow up test for HBV DNA. See Section 9.4.11.2 for details.
Urine pregnancy test	X			X			X			X			X	See Section 9.4.5 and Appendix 6 for details. Females only. To be performed locally.

Notes: Due to blood volume restrictions, some laboratory tests may not be collected. Laboratory samples are recommended to be collected as described in the sponsor-provided weight-based prioritization chart.														
Visit No	V30	V31	V32	V33	V34	V35	V36	V37	V38	V39	V40	V41	V42	Notes
Study Week	W108	W112	W116	W120	W124	W128	W132	W136	W140	W144	W148	W152	W156	
Study Days (Approximately)	756 ± 7d	784 ± 7d	812 ± 7d	840 ± 7d	868 ± 7d	896 ± 7d	924 ± 7d	952 ± 7d	980 ± 7d	1008 ± 7d	1036 ± 7d	1064 ± 7d	1092 ± 7d	
Treatment Visits			X		X	X		X	X		X	X		Treatment visits are intended only for the dispensation and on-site administration of ixekizumab for the participants CCI [REDACTED] who have opted for on-site administration.
Clinical chemistry	X			X		X			X			X		

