5.1.4. Long-Term Extension Period

All procedures during the LTE period will be performed according to the Schedule of Activities (Section 2).

Study Visits

Participants **CCI** will have the option to self-administer ixekizumab at home (or have their caregivers administer it) after both the participants and their caregivers have received the appropriate training (see the SoA and Section 6.1 for details).

The LTE period will include the following on-site visits:

- Regular visits (every 12 weeks, with the exception of Visits 30 and 31/Weeks 108 and 112): both for participants **CCI**
 - During regular visits, ixekizumab will be administered on site to all participants (regardless of their weight)
- Treatment visits (every 4 to 8 weeks starting with Visit 32/Week 116): for participants **CCI** (and those participants **CCI** who have opted to receive ixekizumab on site)

Weight will be recorded, and dosing of ixekizumab will be adjusted during the LTE period according to the participant's weight at each visit.

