See the Schedule of Activities (Section 2) for frequency of pregnancy testing and [Appendix 2](#) and [Appendix 6](#) for additional details about these tests. As per Clinical Trial Facilitation Group (CTFG) recommendation: In each case of delayed menstrual period (over 1 month between menstruations), confirmation of absence of pregnancy is strongly recommended. This recommendation also applies to women of childbearing potential (WOCBP) with infrequent or irregular menstrual cycles.

At Screening

Serum pregnancy tests will be given prior to the first dose of the study intervention for females ≥ 10 years of age (<10 years at investigator discretion) if menarche has been reached or if there is reason to believe the participant is sexually active. Pregnancy test results at screening must be known prior to first dose of the study intervention.

Open-Label Treatment, Open-Label Extension Treatment, and Long-Term Extension Periods

Female participants of childbearing potential (age 10 and older if menarche has been

reached or if there is reason to believe the participant is sexually active, or younger participants per investigator assessment of sexual maturity) will undergo a urine pregnancy test at the clinic on a monthly basis during scheduled visits through Week 264 or the ETV. Additional urine pregnancy testing may be performed at the investigator's discretion. Participants determined to be pregnant will be discontinued from treatment and will no longer be administered study intervention (see Section 8.1.1).

During the Post-Treatment Follow-Up Period

As indicated in the Schedule of Activities, urine pregnancy tests will be collected during each of the post-treatment follow-up visits.

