Women of childbearing potential who are NOT completely abstinent as their preferred and usual lifestyle, or NOT in a same-sex relationship as their preferred and usual lifestyle, must do the following:

Topic	Condition
Pregnancy testing	Have a negative (serum/urine) test result at screening followed by a negative (urine/serum) result within 24 hours prior to treatment exposure. See the protocol Schedule of Activities for subsequent pregnancy testing requirements.
Contraception	
Agree to use 1 highly effective method of contraception, or a combination of 2 effective methods of contraception.
 
These forms of contraception must be used for the duration of the study.

Examples of different forms of contraception:

Methods	Examples
Highly effective contraception (less than 1% failure rate)	
 female sterilization combination oral contraceptive pill progestin-only contraceptive pill (mini-pill) implanted contraceptives injectable contraceptives contraceptive patch (only women <198 pounds or 90 kg) total abstinence vasectomy (if only sexual partner) fallopian tube implants (if confirmed by hysterosalpingogram) combined contraceptive vaginal ring, or intrauterine devices

Effective contraception	
• male or female condoms with spermicide• diaphragms with spermicide or cervical sponges• barrier method with use of a spermicide
◦ condom with spermicide◦ diaphragm with spermicide, or◦ female condom with spermicide 
Note: The barrier method must include use of a spermicide (that is, condom with spermicide, diaphragm with spermicide, or female condom with spermicide) to be considered effective.

Ineffective forms of contraception whether used alone or in any combination	
• spermicide alone• periodic abstinence• fertility awareness (calendar method, temperature method, cervical mucus, or symptothermal)• withdrawal• postcoital douche, or• lactational amenorrhea

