OLE Visits: V8, V11, V14, V17, V20, V23, V26, V29	Use a combination of telephone/telemedicine with use of an acceptable alternative site to perform the assessments required to be done by health care professional, and for the preparation and safe administration of the ixekizumab injection.	Use a combination of telephone/telemedicine with use of an acceptable alternative site to perform the assessments required to be done by health care professional and the delivery of treatment supplies for the actual visit and for the next 2 treatment-only visits (e.g., V8 + V9, V10).
Tx only visits: V9, V10, V12, V13, V15, V16, V18, V19, V21, V22, V24, V25, V27, V28	Use a combination of telephone/telemedicine for follow up with use of an acceptable alternative site for the safe administration of the injection for participants under ixekizumab treatment arm.	Telephone/telemedicine for follow up. Participants would have received additional treatment supplies in the previous regular visit.
LTE Visits: V30, V31,	Use a combination of telephone/telemedicine with use of an acceptable alternative site to	Use a combination of telephone/telemedicine with use of an acceptable alternative site to perform the

Visit(s)	Guidance	
V33, V36, V39, V42,V45, V48, V51, V54, V57, V60, V63, V66, V69	perform the assessments required to be done by health care professionals, and for the preparation and safe administration of the ixekizumab injection.	assessments required to be done by health care professionals and the delivery of treatment supplies for the actual visit and for the next 2 treatment-only visits (e.g., V31 + V32, V34).
LTE Tx Visits Only: V32, V34, V35, V37, V38, V40, V41, V43, V44, V46, V47, V49, V50, V52, V53, V55, V56, V58, V59, V61, V62, V64, V65, V67, V68		Telephone/telemedicine for follow up. Participants would have received additional treatment supplies in the previous regular visit.
ETV	Sites may use telephone/telemedicine.	Sites may use telephone/telemedicine.
Follow-up (V801-V803)	Telephone/telemedicine or use of an acceptable alternative site.	Telephone/telemedicine or use of an acceptable alternative site.

Abbreviations: ETV = early termination visit; LTE = long-term extension; OLE = open-label extension; OLT = open-label treatment; Tx = treatment; V = visit.

Any required procedures that cannot be conducted at that time should be conducted as soon as possible thereafter, using an unscheduled visit if necessary.

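### Protocol 9.4.5 requires monthly clinic urine pregnancy tests through Week 264, but the LTE schedule tables mark a test only every 12 weeks (14 of 40 visits).

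*Protocol*

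**What the plan says.** Protocol 9.4.5 has one paragraph, under a heading that names the OLT, OLE and LTE, on urine tests during treatment. It requires a clinic test "on a monthly basis during scheduled visits through Week 264 or the ETV" and says that a pregnant participant stops study drug.

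The same section opens with a pointer: "See the Schedule of Activities (Section 2) for frequency of pregnancy testing". Appendix 6 does likewise: "See the protocol Schedule of Activities for subsequent pregnancy testing requirements".

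In the LTE part of the Schedule, the urine pregnancy row is marked at Visits 30, 33, 36 and every third visit up to 69. The notes beside that row differ between tables. Tables RHCG.2.3 and 2.6 send the reader back: "See Section 9.4.5 and Appendix 6 for details. Females only. To be performed locally". Tables RHCG.2.4 and 2.5 refer to Section 5.1.1, which deals with testing before the first dose and gives no LTE frequency.

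The LTE has two kinds of visit. Section 5.1.4 describes "Regular visits (every 12 weeks, with the exception of Visits 30 and 31/Weeks 108 and 112", attended by all participants. The tables also carry a second kind: "Treatment visits are intended only for the dispensation and on-site administration of ixekizumab for the participants" who are dosed on site. Appendix 8 separates them in the same way, with one row starting "LTE Visits: V30, V31" and another starting "LTE Tx Visits Only: V32, V34, V35, V37, V38".

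**The concern.** The text and the tables give two different test frequencies for the same participants over the same 160 weeks. The cross-references run in a circle: 9.4.5 sends the reader to the Schedule for frequency, and two of the four LTE tables send the reader back to 9.4.5. A site can reasonably follow the tables, but it then departs from a sentence that states a requirement.

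The monthly sentence does not look like text left over from before the LTE was added. It names the LTE and runs to Week 264, while Section 5.1.2, on the OLT, still ends its monthly rule at Week 104.

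What is at stake is how long a pregnancy could go undetected while dosing continues. Pregnancy requires discontinuation (Sections 8.1.1 and 9.4.5), and Section 3.3 says human data are insufficient to establish the safety of ixekizumab in pregnancy. There is also a conduct risk: sites that follow the tables could be recorded as deviating from 9.4.5.

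**Working it through.** The check is a count of the marks in the urine pregnancy test rows of Tables RHCG.2.1 to 2.6, with each visit mapped to its study week. ETV and post-treatment follow-up columns are left out of the LTE count.

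**Through Week 104**

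- OLT (Table 2.1): Visits 2, 4, 5, 6 and 7, that is Weeks 0, 4, 8, 12 and 16: 5 tests.
- OLE (Table 2.2 and its continuation): every visit from 8 to 29, Weeks 20 to 104: 13 + 9 = 22 tests.
- Total 5 + 22 = 27 tests, all 4 weeks apart. The monthly rule is met.

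**LTE, Visits 30 to 69 (Weeks 108 to 264)**

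| Table | Visits | Tests marked | Treatment visits |
|---|---|---|---|
| 2.3 | 30–42 (13) | 5 (V30, 33, 36, 39, 42) | 7 |
| 2.4 | 43–54 (12) | 4 (V45, 48, 51, 54) | 8 |
| 2.5 | 55–66 (12) | 4 (V57, 60, 63, 66) | 8 |
| 2.6 | 67–69 (3) | 1 (V69) | 2 |
| Total | 40 | 14 | 25 |

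- The marked tests fall at Weeks 108, 120, 132 and so on to 264. All 13 gaps are 12 weeks.
- Unmarked visits: 40 − 14 = 26.
- Of these, 25 are treatment visits, and Appendix 8 lists the same 25. The remaining one is Visit 31 (Week 112). It carries no treatment-visit mark, Section 5.1.4 names it with Visit 30, and Appendix 8 groups it with the regular LTE visits.

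**By route of dosing**

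- On site throughout: 40 visits attended, 26 without a marked test.
- At home throughout: 40 − 25 = 15 regular visits attended, 14 with a test and 1 (Visit 31) without.

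**Doses between tests**

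- Under the tables: test and dose at Visit 33, doses at Visits 34 and 35, next test at Visit 36. Two doses are given without a new test.
- Under monthly testing at each dosing visit: none.
- Difference: 2 − 0 = 2 doses.

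**The case against.** The strongest reply is that the documents say which source governs. Both 9.4.5 and Appendix 6 defer to the Schedule for frequency, and the four LTE tables agree with one another. On that reading the fault is one over-extended sentence, and a site working from the tables has a clear instruction. Twelve-weekly testing also suits at-home dosers, who have no clinic visit between regular visits. Other safeguards exist: the contraception or abstinence rule in inclusion criterion 5, the recommendation to test after a delayed period, and extra tests at the investigator's discretion.

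Part of this stands. Following the tables is reasonable, 12-weekly testing may be what was intended, and the scheduled test is one safeguard among several. For at-home dosers the gap between tests comes from the visit design, so the two-dose difference bears mainly on those dosed on site. The size of that group is not given.

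The conflict remains, however. Two of the LTE tables refer back to 9.4.5. In the paragraph on post-treatment follow-up, 9.4.5 defers explicitly to the Schedule; the sentence covering the LTE contains no such deferral. Reading its reference to scheduled visits as 12-weekly would leave the word monthly without meaning. Neither convenience nor at-home dosing explains Visit 31. Nor is testing at treatment visits impractical, since the OLE tables already require it there.

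The Week 104 limit in 5.1.2 is true under either frequency, so it does not settle the LTE. The 12-weekly contingency interval in Appendix 8 applies from Week 16 onward, including the OLE, where the Schedule tests every four weeks. It is weak evidence of what was intended.

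**Conclusion.** The inconsistency is real. The text requires monthly tests in the LTE, and the tables provide 14 tests at 40 four-weekly visits. The shortfall is 26 visits for a participant dosed on site throughout and one visit (Visit 31) for a participant dosing at home throughout. Section 9.4.5 does not say what applies to at-home dosers between regular visits.

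Following the tables allows up to two more doses between tests than monthly testing would. That figure assumes dosing every four weeks as scheduled and no unscheduled test in between.

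The matter should be corrected but is contained. It concerns females of childbearing potential in the LTE, whose number the documents do not give, and it touches neither the primary endpoint nor its analysis. The documents do not settle which frequency was intended.

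**What to change.** The sponsor should confirm the intended LTE frequency and make 9.4.5 and the tables agree.

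- **If monthly:** mark the urine test at Visit 31 for all females of childbearing potential, and at the LTE treatment visits for those who attend them for on-site dosing. State in 9.4.5 what applies to at-home dosers between regular visits. The simpler choice is 12-weekly testing with a stated reason. The alternative is a home urine test reported to the site before each dose, which would need the clinic wording changed and the adolescent's confidentiality addressed. Cost: marks in four schedule tables and up to 26 extra urine kits per participant dosed on site throughout. An at-home doser needs 1 extra kit, plus up to 25 more only if home testing is chosen.
- **If 12-weekly for everyone in the LTE:** amend the 9.4.5 sentence to monthly through Week 104 and every 12 weeks thereafter, and leave the tables as they are. Cost: one sentence.

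In either case, point the notes in Tables RHCG.2.4 and 2.5 to 9.4.5, since Section 5.1.1 does not cover LTE testing.

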9.4.6. Chest X-Ray and Tuberculosis Testing

A posterior-anterior view chest x-ray will be obtained, unless the x-ray or results from a chest x-ray obtained within 6 months prior to the study are available or the results from the TB testing (QuantiFERON® TB Gold, T-Spot or PPD) if aligned with local practice.

The chest x-ray or results will be reviewed by the investigator or designee and considered along with the participant's medical history, assessment of risk factor for *M. tuberculosis* infection and physical examination to exclude participants with active TB infection.

Participants will be tested as indicated in the Schedule of Activities (Section 2) for evidence of *M. tuberculosis* infection.

TB testing - QuantiFERON® TB Gold will be the preferred testing option for TB. The QuantiFERON® TB Gold test may be performed locally or centrally. If the QuantiFERON®-TB Gold test is indeterminate (not negative), 1 retest is allowed. If the retest for the QuantiFERON®-TB Gold test is indeterminate (not negative), the participant is excluded from enrollment in the study.

In countries where the QuantiFERON®-TB Gold test is not available or due to investigator's judgement (e.g., need to reduce the volume of blood collected), the T-Spot or PPD test may be used. In the case of selecting the PPD test, the participant must return within 48 to 72 hours to read the skin test.

A positive PPD skin test response for this study is defined as ≥ 5 -mm induration between 48 and 72 hours after PPD application, regardless of Bacillus Calmette-Guérin vaccination history.

Participants with documentation of a negative QuantiFERON®-TB Gold test or T-Spot result or PPD result within 3 months prior to baseline (Week 0; Visit 2) are not required to have a TB test at Visit 1 unless medical history, including assessment for TB infection risk factors, chest x-ray, or physical examination indicate that testing should be done.

Documentation of this test result must include a record of the size of the induration response (< 5 -mm induration) or the laboratory report of the QuantiFERON®-TB Gold test or T-Spot result. A PPD test recorded as negative without documenting the size of induration will require a retest.

Participants with a PPD skin test ≥ 5 mm induration or a positive QuantiFERON®-TB Gold or T-Spot test but no evidence of active TB, and participants who have a documented history of a positive TB test but no documented history of completion of a full, appropriate latent TB treatment course, who are assessed as having latent TB infection may be re-screened 1 time and may be enrolled without repeating a QuantiFERON®-TB Gold, T-Spot or PPD test if the following conditions are met:

- after receiving at least 4 weeks of appropriate latent TB infection therapy with no evidence of hepatotoxicity (ALT/AST must remain $\leq 2 \times$ ULN) upon retesting of serum ALT/AST prior to randomization,
- commitment by the participant and the caregiver for the participant to complete a full course of standard prophylaxis for TB, and
- meet all other inclusion/exclusion criteria for participation.

Such participants must complete appropriate latent TB infection therapy to remain eligible for continued study participation. If rescreening occurs within 6 months of the screening chest x-ray, a repeat of chest x-ray for considering enrollment is not required.

If a participant with a positive QuantiFERON®-TB Gold or T-Spot or PPD is fully assessed by the investigator and the investigator determines that the participant has no risk factors for and no symptoms or signs of *M. tuberculosis* infection, the investigator may contact Lilly Medical to discuss the possibility of a false-positive test result.

Participants with positive TB test results on file: Participants with a documented prior history of a positive TB test and participants who have a documented history of completion of an appropriate TB treatment regimen for latent or active TB should not have a TB test performed at Visit 1. Such participants with no history of re-exposure to TB since their treatment was completed and no evidence of active TB are eligible to participate in the study. Participants who have had household contact with a person with active TB are excluded unless an appropriate and documented course of prophylaxis for TB was completed.

Participants are to be monitored on a regular basis for any symptoms or signs of active TB and for any new risk factors for TB infection, with full medical evaluation including TB testing when medically indicated. Participants that exhibit symptoms of active TB should be referred to a specialist in the care of participants with TB.

Any clinically significant findings from chest x-rays and/or TB testing that result in a diagnosis and that occur after the participant signs the ICF should be reported to Lilly or its designee as an AE via eCRF.

